6.2. Determination of Sample Size

The sample size was calculated by evaluating whether the Al algorithm achieved a success rate of more than 90%, considering 5% Type-I error, 80% power, and different effect sizes listed below.

Prop	ortion	Proportion					
		Given H0	Given H1	Target	Actual		Reject H0
Power	N	(P0)	(P1)	Alpha	Alpha	Beta	If Z>=This
0,8033	5341	0,9000	0,9100	0,0500	0,0511	0,1967	1,6449
0,8002	2286	0,9000	0,9150	0,0500	0,0520	0,1998	1,6449
0,8015	1255	0,9000	0,9200	0,0500	0,0525	0,1985	1,6449
0,8004	778	0,9000	0,9250	0,0500	0,0530	0,1996	1,6449
0,8012	523	0,9000	0,9300	0,0500	0,0541	0,1988	1,6449
0,8047	376	0,9000	0,9350	0,0500	0,0545	0,1953	1,6449
0,8092	284	0,9000	0,9400	0,0500	0,0539	0,1908	1,6449
0,8076	212	0,9000	0,9450	0,0500	0,0565	0,1924	1,6449
0,8004	164	0,9000	0,9500	0,0500	0,0553	0,1996	1,6449

Considering the situation marked in the table above as an example, if at least 778 people are included in the study, the case that the Al algorithm will achieve at least 2.5% above the 90% level can be detected at 80% power and 5% type-1 error level. If the success rate of the Al algorithm increases at a level of 2.5% or less from 90%, this difference will not be statistically significant. (Annex-1 Analysis Plan)

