3.5. Success Criteria of Study

Three different doctors will evaluate the volunteer's fundus images taken from fundus cameras and will make a decision about the presence of DR: Not more than Mild DR, More than mild DR (mtmDR), and Vision-threatening DR (vtDR). Decisions will be made by majority vote. The doctors' decision will be Ground Truth for us.

EyeCheckup will decide for both eyes of each volunteer. If it is the same as the doctors' decision, this decision will be considered correct.

Total correct number / Total number of eyes = Success rate

Our criteria for successful completion of the clinical trial: Success rate > 90%

EC-2021DR-TR DETECTION AND CLASSIFICATION OF DIABETIC RETINOPATHY FROM POSTERIOR POLE IMAGES WITH A DEEP LEARNING MODEL

At the same time, the Specificity and Sensitivity values should be calculated separately for mtmDR and vtDR and each should be above 90%.

Eye doctors (Normal, mtmDR, vtDR) make their decisions according to the ETDRS guidelines. Main signs to check for: Microaneurysms, Intreretinal hemorrhages (Intraretinal hemorrhage), Venous beading, IRMA, Neovascularization, Intravitreal hemorrhage, Preretinal hemorrhage

3.6. The benefit of the Research, Possible risks and precautions to be taken against harm:

Benefits;

According to the 2018 data from the World Health Organization, 285 million people worldwide have a visual impairment. It is known that more than 80% of all visual disorders can be prevented or treated. The retinal examination should be performed by an ophthalmologist and/or retinal specialist in order to prevent retinal-related visual disorders by making an accurate diagnosis, but people only consult an ophthalmologist when they feel any discomfort. Typically, by the time symptoms appear, the disease has reached advanced stages and requires a variety of expensive medical and surgical treatments. Unfortunately, at this stage, the disease often results in severe and permanent visual impairment and vision loss.

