ANNEX-1 ANALYSIS PLAN

The diagnosis of the patients will be made by 3 doctors by evaluating the images and a joint diagnosis decision will be made by combining the diagnosis made by the doctors for each patient. This diagnosis will be considered the "Gold Standard" for the study. With the developed Al algorithm, it will be investigated to what extent the diagnosis made by the doctors can be predicted. The Al algorithm developed for the diagnosis of DR is expected to achieve a success rate of 90% or more. A success above this level will show that the developed Al algorithm will be usable. For this purpose, whether the Al algorithm achieves a success rate of 90% or more will be investigated with the one-way hypothesis pair given below.

$$H_0: P = 0.90 H_1: P > 0.90$$

The sample size was calculated by evaluating whether the Al algorithm achieved a success rate of more than 90%, considering 5% Type-I error, 80% power, and different effect sizes listed below.

Prop	ortion	Proportion					
_		Given H0	Given H1	Target	Actual		Reject H0
Power	N	(P0)	(P1)	Alpha	Alpha	Beta	If Z>=This
0,8033	5341	0,9000	0,9100	0,0500	0,0511	0,1967	1,6449
0,8002	2286	0,9000	0,9150	0,0500	0,0520	0,1998	1,6449
0,8015	1255	0,9000	0,9200	0,0500	0,0525	0,1985	1,6449
0,8004	778	0,9000	0,9250	0,0500	0,0530	0,1996	1,6449
0,8012	523	0,9000	0,9300	0,0500	0,0541	0,1988	1,6449
0,8047	376	0,9000	0,9350	0,0500	0,0545	0,1953	1,6449
0,8092	284	0,9000	0,9400	0,0500	0,0539	0,1908	1,6449
0,8076	212	0,9000	0,9450	0,0500	0,0565	0,1924	1,6449
0,8004	164	0,9000	0,9500	0,0500	0,0553	0,1996	1,6449

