Considering the situation marked in the table above as an example, if at least 778 people are included in the study, the case that the AI algorithm will achieve at least 2.5% above the 90% level can be detected at 80% power and 5% type-1 error level. If the success rate of the AI algorithm increases at a level of 2.5% or from to 90%, this difference will not be statistically significant. From this point of view, at least how high the AI algorithm will be above the threshold value should be determined and the sample size should be taken into account over this difference. For example, the 91% performance of the AI algorithm compared to the threshold value and investigating the statistical significance of the 1% difference may not be clinically appropriate, however, an increase of 2% or more may be considered clinically significant. At this point, it is important to determine the minimum effect size (distance to 90% level) that should be taken into account in order to

demonstrate clinical success (in other words, the AI algorithm performs more than 90%). (If it is necessary to evaluate the graph given above, the red distribution is the reference point for clinical success, and the blue distribution is the distribution showing how much the AI algorithm can exceed this threshold value. The effect size is the distance between the red and blue distributions.)

Statistical Analysis Plan

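### The plan says a gain of 2.5 points or less over 90% will not be significant, but its own test is significant from about 1.8 points at N=778 and 1.7 at N=900

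*Combined protocol and SAP*

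**What the plan says.** Section 6.2 sizes the study for a success rate above 90%, "considering 5% Type-I error, 80% power, and different effect sizes listed below". Annex-1 gives the hypotheses, "H_0: P = 0.90 H_1: P > 0.90", as a one-sided pair. Each of the nine table rows carries the same rejection rule, Z at or above 1.6449. The row used as the example has N=778, a null rate of 0.90, an alternative of 0.925, actual alpha 0.0530 and power 0.8004.

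Section 6.2 then makes two statements in succession. First, with at least 778 people, a gain of at least 2.5 points over 90% "can be detected at 80% power and 5% type-1 error level". Second, if the success rate "increases at a level of 2.5% or less from 90%, this difference will not be statistically significant".

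Annex-1 repeats both. Its second sentence is corrupted ("increases at a level of 2.5% or from to 90%, this difference will not be statistically significant") but is very probably the same statement. Annex-1 then argues from it that a minimum effect size must be settled, and offers as an example that "an increase of 2% or more may be considered clinically significant". Planned enrolment is 900 (section 6.1). Section 3.5 counts eyes, not people: "Total correct number / Total number of eyes = Success rate".

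**The concern.** The gain a test detects with 80% power is always larger than the smallest observed gain that reaches significance. If the truth lay exactly on the significance boundary, the test would reject only about half the time, so the design effect has to lie above it. The second sentence treats the two as one number.

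At exactly 2.5 points it also contradicts the sentence before it. The same gain cannot be detectable with 80% power and also be one that will not be significant.

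A success rate above 90% is what the trial sets out to show. If the result falls between the true cut-off and 92.5%, the test rejects the null hypothesis while the protocol states that the gain is not significant. An assessor could hold that sentence against a positive result.

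**Working it through.** **Inputs.** Null rate 0.90, critical value 1.6449, and N=778 with alternative 0.925: table in section 6.2, repeated in Annex-1. One-sided hypotheses: Annex-1. Planned N=900: section 6.1.

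**Step 1: reproduce the plan's figure.** Take Z = (k/N − 0.90) / √(0.90 × 0.10 / N) for k correct out of N, find the smallest k with Z ≥ 1.6449, and compute exact binomial tail probabilities.

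- N=778: the standard error is √(0.09/778) = 0.010756. For k=713, Z=1.530; for k=714, Z=1.649. The cut-off is 714.
- P(X ≥ 714) is 0.0530 at a true rate of 0.90 and 0.8004 at 0.925. Both match the printed row.
- All nine rows reproduce to four decimals for actual alpha and power. With the observed rate in the variance instead, the N=778 row does not (alpha 0.0681, power 0.8352). The null-variance Z rule is therefore the one behind the table.

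**Step 2: smallest significant observed gain.**

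- N=778: 714/778 = 91.77%, a gain of 1.77 points (continuous boundary 1.6449 × 0.010756 = 0.0177).
- N=900: the standard error is √(0.09/900) = 0.0100. For k=824, Z=1.556; for k=825, Z=1.667. The cut-off is 825/900 = 91.67%, a gain of 1.67 points (continuous boundary 1.64).

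**Step 3: results the sentence misclassifies.** A gain of 2.5 points is 0.925 × 778 = 719.65 or 0.925 × 900 = 832.5. Counts of 714 to 719 out of 778, and of 825 to 832 out of 900, are significant but described as not. The upper ends are not borderline: 719/778 has Z=2.25 and exact one-sided p=0.012; 832/900 has Z=2.44 and p=0.007.

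**Step 4: reading the gain as the true rate.** Probability that the test is significant:

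| True rate | N=778 (714 or more) | N=900 (825 or more) |
|---|---|---|
| 91.0% | 25% | 26% |
| 91.5% | 42% | 46% |
| 92.0% | 62% | 67% |
| 92.5% | 80% | 84% |

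**Step 5: other tests and units.**

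- Exact binomial test at one-sided 0.05: 715/778 (+1.90 points) and 826/900 (+1.78).
- Critical value 1.96, in case 0.05 is meant as two-sided: 717/778 (+2.16) and 828/900 (+2.00).
- Eyes as the unit, assuming 900 people with two eyes each and the standard error multiplied by √(1+ρ), where ρ is the between-eye correlation (not given in the documents): 1641/1800 (+1.17) at ρ=0, 1646/1800 (+1.44) at ρ=0.5, 1650/1800 (+1.67) at ρ=1.

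None of these cut-offs reaches 2.5 points.

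**The case against.** The strongest reply is that the sentence comments on a worked example and is not a decision rule. The success criterion sits in section 3.5, which has no 2.5-point threshold. The hypotheses and critical value are correct, and the analyst's p-value will come from the test, not from this sentence. No sample size or table entry changes. All of that is true, and it limits the repair to wording. It does not make the sentence harmless: it tells readers which results of the main test count as significant, gets that wrong, and Annex-1 reasons onward from it.

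A second objection concerns the replacement figures. Section 6.1 and the statistical analysis plan in Annex-1 leave the test open among several, and the Z rule comes only from the sample-size table. Its actual alpha at 825/900 is 5.1%, slightly above the stated 0.05. An exact binomial test at one-sided 0.05 would need 826/900 (actual alpha 4.0%), with power 81% at a true 92.5% and 63% at 92%. This stands as a caution: any figures put in must name the test.

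A third is that the shortfall for a 2-point gain can already be inferred, since the table lists N=1255 for an alternative of 92%, and Annex-1 offers 2 points only as an example. That is fair, but the text nowhere states the power that 900 participants give for that gain.

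**Conclusion.** The sentence is wrong on either reading. As an observed gain, the threshold under the plan's own rule is 1.77 points at N=778 and 1.67 at N=900, not 2.5. As a true gain, the plan rules out significance where the test has a 62% to 84% chance of reaching it, for true rates of 92% to 92.5% at those two sample sizes.

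The cut-offs rest on the null-variance Z rule, which the table confirms. The conclusion does not depend on that choice: exact, stricter and eye-level versions all stay below 2.5 points. The eye-level range, 1.2 to 1.7 points, rests on assumed values of the between-eye correlation and on two evaluable eyes per person.

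The fault is one of interpretation. N=778, the table and the planned 900 stand as printed. The figures concern overall agreement only and say nothing about the separate sensitivity and specificity criteria for mtmDR and vtDR.

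**What to change.** Delete the sentence in section 6.2 and in Annex-1. Replacement text, provided the Z rule is kept as the test:

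> On the person-level calculation, with 900 participants and the one-sided rule Z ≥ 1.6449, an observed success rate of 825/900 (91.7%) or more is significant (actual alpha 5.1%). Power is 84% if the true rate is 92.5% and 67% if it is 92%. These figures cover overall agreement only, not the separate sensitivity and specificity criteria.

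If an exact binomial test at one-sided 0.05 is chosen instead, give 826/900, actual alpha 4.0%, and power of 81% and 63%.

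Describe 2.5 points as the design effect size, and add in Annex-1 that the 2-point gain used there as an example does not have 80% power on this person-level calculation. If the analysis counts eyes, as section 3.5 does, give separate figures that allow for between-eye correlation and state the value assumed.

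The cost is wording in two places, with no change to the sample size. The plan would then say openly that person-level power for a true 2-point gain is 67%, and an eye-level analysis would need a stated correlation.

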6.3. Measurement and evaluation of effectiveness parameters

The Diabetic Retinopathy diagnosis of EyeCheckup and Diabetic Retinopathy diagnosis results made by specialist doctors will be compared, and evaluation and statistical analysis will be made by the researchers.

7. STUDY MANAGEMENT

7.1. Recording Data

The site coordinator will ensure that all data obtained during patient visits is quickly entered into the electronic case report form in accordance with other specific information provided. The explanation for not entering any required data should be stated on the appropriate page.

The site coordinator and the principal investigator must sign with a digital signature to confirm the accuracy of the information entered in the electronic case report form, thus declaring that they take responsibility for the accuracy of all case record data.

7.2. Protocol Changes

If a change to the protocol is required, it will be submitted to the ethics committee for approval, and the investigator will ensure that the change is referenced and approved in a timely manner.

7.3. Storage of operating data

[figure not shown]
The investigator must retain all legal/study documents, signed informed consent forms (BGOF), electronic case report forms, and source documents for ten years after study completion.

As the owner of the data, the coordinating investigator must keep all other documentation of the study for as long as the product is available. These documents and procedures will include all written reflections on the protocol and procedures, original copies of case report forms for each study patient, any raw/source data provided by the investigator, the final report, and inspection certificates, if available.

It will be guaranteed that the highest possible accuracy is achieved during the processing of the data. The collected data is compiled and analyzed within the framework of statistical models. According to this analysis, a Clinical Research Report is prepared.

7.4. Sharing and publishing results

All information obtained as a result of the study should be treated as CONFIDENTIAL. Before the conclusion of the abstract, article, or visual presentation, it is acceptable that the results of this study will be shared in scientific meetings or publications if the researchers and the coordinator EC-2021DR-TR DETECTION AND CLASSIFICATION OF DIABETIC RETINOPATHY FROM POSTERIOR POLE IMAGES WITH A DEEP LEARNING MODEL

researcher mutually agree on the contents and conclusion comments. This agreement also applies to any changes requested later by reviewers or journal editors.

7.5. Patient Confidentiality

All personal information collected and processed in accordance with the purpose of this study will be handled by the researcher and their team, with appropriate measures to ensure the confidentiality of this data, and in accordance with applicable national and/or local laws and regulations regarding personal data protection.

In our clinical research, the records that will show that the identity of the volunteers are kept confidential, and not disclosed to the public, and the identity of the volunteers remains confidential even if the research results are published.

Viewers, pollers, the Ethics Committee, the Ministry of Health, and other relevant health authorities can directly access the original medical records. By signing the informed voluntary consent form, only the persons and institutions mentioned are granted access.

8. PERSON AND/OR INSTITUTION WITH DIRECT ACCESS AUTHORITY

There is no person and/or institution with direct access authority. The only authorized institution is URAL Telekom.

9. ETHICAL ASSESSMENTS

9.1. Examining the Ethical Issues of the Study

Due to its design, this study does not interfere with the diagnosis and treatment approaches of physicians. The procedures performed within the scope of the study will be carried out in accordance with the revised Declaration of Helsinki and the ethical rules determined by all national and international regulations.

Ethics committee and TR Ministry of Health approval letters will be sent to the participating institution before the study is started.

The formation of Ethics Committees should comply with the relevant Turkish laws, regulations, and guidelines.

Fidelity: Data will be obtained from observations using scientific methods only. Interpretation and evaluation of data will be based on scientific methods. Any unobtained result will not be shown as a research result.

No Harm in Scientific Research: Volunteers will not be harmed in any way during the research process. Volunteers will be informed about the study and a minimum notification consent form will be signed.

Responsibilities and Rights: The principal investigator will inform the volunteers about **the** research findings and warn them about possible harmful practices.

EC-2021DR-TR DETECTION AND CLASSIFICATION OF DIABETIC RETINOPATHY FROM POSTERIOR POLE IMAGES WITH A DEEP LEARNING MODEL

Authors: The names of all researchers are published in proportion to their contributions. The names of people who did not contribute effectively to the planning, execution, and preparation of the research cannot be published in the list of authors.

Citations and Citations: The books, journals, and all kinds of citation sources used in the publication of the research results will be indicated. Any work and information cannot be used or published without permission and reference.

9.2. Be Informed

Written informed consent will be obtained from each patient prior to entry into the study, that is, prior to any screening evaluation or any study-related activity. For patients whose written informed consent cannot be obtained, the patient's legal guardian or guardian must sign the informed consent form. This form will be received from each individual in accordance with the recommendations of the revised Declaration of Helsinki. An independent staff member will explain the form, purpose, and risks of the study. The patient will then be given sufficient time to consider the study before deciding whether or not to participate. In all cases, the patient will be given a copy of the signed and voluntary informed consent form.

[figure not shown]
10. FINANCE AND INSURANCE

EyeCheckup is a software, it has no contact or interaction with the patient. Our study will be performed with fundus images taken from 900 volunteer patients diagnosed with diabetes from CE-marked fundus cameras. The EyeCheckup software will not be tested directly on the patient and has no contact with the patient. It will be installed on the computer and will evaluate the photos using artificial intelligence algorithms on the cloud.

Since our EyeCheckup software does not have an EC certificate, all volunteers who will participate in the research will be insured by Ural Telekom.

11. PUBLICATION POLICY

- All citations used in the article are referenced.
- The research result in the article is presented openly and honestly, without fabrication, false or inappropriate data manipulation.
- Scientific contribution to the article is guaranteed.
- Names of people who contributed to the article and consent to be named as co-authors are included in the article.
- If deemed necessary, access to the data sets in the article is provided.
- The author is responsible for the opinions expressed in the article.

ANNEX-1 ANALYSIS PLAN

The diagnosis of the patients will be made by 3 doctors by evaluating the images and a joint diagnosis decision will be made by combining the diagnosis made by the doctors for each patient. This diagnosis will be considered the "Gold Standard" for the study. With the developed Al algorithm, it will be investigated to what extent the diagnosis made by the doctors can be predicted. The Al algorithm developed for the diagnosis of DR is expected to achieve a success rate of 90% or more. A success above this level will show that the developed Al algorithm will be usable. For this purpose, whether the Al algorithm achieves a success rate of 90% or more will be investigated with the one-way hypothesis pair given below.

$$H_0: P = 0.90 H_1: P > 0.90$$

The sample size was calculated by evaluating whether the Al algorithm achieved a success rate of more than 90%, considering 5% Type-I error, 80% power, and different effect sizes listed below.

Prop	ortion	Proportion					
_		Given H0	Given H1	Target	Actual		Reject H0
Power	N	(P0)	(P1)	Alpha	Alpha	Beta	If Z>=This
0,8033	5341	0,9000	0,9100	0,0500	0,0511	0,1967	1,6449
0,8002	2286	0,9000	0,9150	0,0500	0,0520	0,1998	1,6449
0,8015	1255	0,9000	0,9200	0,0500	0,0525	0,1985	1,6449
0,8004	778	0,9000	0,9250	0,0500	0,0530	0,1996	1,6449
0,8012	523	0,9000	0,9300	0,0500	0,0541	0,1988	1,6449
0,8047	376	0,9000	0,9350	0,0500	0,0545	0,1953	1,6449
0,8092	284	0,9000	0,9400	0,0500	0,0539	0,1908	1,6449
0,8076	212	0,9000	0,9450	0,0500	0,0565	0,1924	1,6449
0,8004	164	0,9000	0,9500	0,0500	0,0553	0,1996	1,6449

Considering the situation marked in the table above as an example, if at least 778 people are included in the study, the case that the AI algorithm will achieve at least 2.5% above the 90% level can be detected at 80% power and 5% type-1 error level. If the success rate of the AI algorithm increases at a level of 2.5% or from to 90%, this difference will not be statistically significant. From this point of view, at least how high the AI algorithm will be above the threshold value should be determined and the sample size should be taken into account over this difference. For example, the 91% performance of the AI algorithm compared to the threshold value and investigating the statistical significance of the 1% difference may not be clinically appropriate, however, an increase of 2% or more may be considered clinically significant. At this point, it is important to determine the minimum effect size (distance to 90% level) that should be taken into account in order to

demonstrate clinical success (in other words, the AI algorithm performs more than 90%). (If it is necessary to evaluate the graph given above, the red distribution is the reference point for clinical success, and the blue distribution is the distribution showing how much the AI algorithm can exceed this threshold value. The effect size is the distance between the red and blue distributions.)

Statistical Analysis Plan

The diagnostic performance of the AI algorithm will be evaluated with reference to the decisions made by the doctors. Gold standard test results will be obtained based on the diagnosis provided by three different doctors. At this stage, the compatibility between the diagnosis from the doctors will be evaluated according to the Kappa statistics, and the similarity of the diagnosis made by the doctors with each other will be examined. The diagnoses of the patients will then be evaluated together with the results of the AI algorithm, and performance measures of the AI algorithm (sensitivity, selectivity, positive predictive value, negative predictive value, overall accuracy, etc.) will be obtained. Whether the performances of the AI algorithm are clinically acceptable or not will be evaluated with ratio tests (single sample population ratio significance test, Fisher Exact test, Chi-square tests, etc.) according to the threshold values to be determined by experts. A data analysis software will be selected amongst various softwares (R, SPSS, TURCOSA, Stata, etc.) to do the statistical analysis in accordance with the purpose. For statistical analysis, the level of significance will be taken as 0.05.
